**Document History**

Document	Version Date	Summary of Changes
MYL-1501D-3003 Clinical Trial Protocol	1.0, 09-Oct-2015	N/A
MYL-1501D-3003 Clinical Trial Protocol Amendment	2.0, 06-May-2016	
 
• Approval Signatures page: Version and effective date are changed. Sponsor’s personnel and designations changed (Approval Signatures).
 
• In the section Contact Details For Reporting Serious Adverse Events, the sentence “Any SAE occurring in a subject from consent until 28 days after the last dose of the study drug must be reported” has been replaced with “Any SAE occurring in a subject from consent until his/her last study visit/phone visit (scheduled or unscheduled) must be reported”.
 
• The Synopsis and section 2.1, the wording of the Primary and the Secondary objective of Immunogenicity, were modified for clarity.
 
• The Synopsis and sections 3.1 and 9.1, number of patients (from estimated 110 patient to estimated 138 patients) and sites (from estimated 80 to estimated 70) were modified.
 
• The Synopsis, Schedule of Activities, Study Flowchart [Figure 1], Sections 1.1, 3, 3.1, 6.1, 6.2, table 3 were modified to include additional treatment period, weeks 24-36.
 
• The following changes made to the Schedule of Activities:               
 
• Clarification made regarding certain data captured in MYL-GAI-3001 that will be reused in MYL-1501D-3003 (Footnotes #8 and #11).
 
• Clarification on informed consent made (Footnote #3).
 
 
 

		

• Clarification made regarding ongoing adverse events from MYL-GAI-3001 (Footnote #8).

• Clarification made that allergic reactions, AEs and SAEs will be captured during the follow up period (Footnote #12).

• Sections 1.1, Background and Rationale. Explanation and rationale for the study design change is provided.

• Section 5.4 - Clarification made regarding opened and expired study medication.

• Synopsis and Section 6.2. To minimize missing data, clarification added that patients who have been prematurely withdrawn from treatment will be followed up until the 40 week follow-up call in case consent is provided.

• Schedule of Activities, Section 7.3, Table 4. Blood collection for immunogenicity analysis added at 4, 26, 28, 32 and 36 weeks.

• Sections 7.3 and 7.4.10. Details of central laboratories for immunogenicity and safety analyses modified.

• Sections 7.3.1 and 7.3.2. Methodology for immunogenicity assessments were modified.

• Sections 7.4.1 and 7.4.2. Clarifications made regarding medical history and prior and concomitant medications.

• Section 7.5.4. Clarification made regarding dilated ophthalmoscopy/retinal photography testing.

• Section 8.3. Clarification made regarding the collection period for AEs and SAEs; text on reporting for withdrawn patients removed, as this is covered in.

• Section 9. Modifications made throughout the data analysis/statistical methods section.

• Section 9.2.1. Text regarding primary

--	--	--

		
endpoint modified to accommodate addition of treatment period.
 

• Section 9.2.2. The primary analysis population changed from ITT to mITT; descriptive text on analysis populations added.

• Section 9.7. The primary efficacy analysis changed from non-inferiority to equivalence.

• Investigator Agreement Page added to body of protocol (previously appended separately).

• Minor editorial and formatting corrections made throughout the protocol.

--	--	---

### **CONTACT DETAILS FOR REPORTING SERIOUS ADVERSE EVENTS**

A serious adverse event (SAE) is any event which is fatal or life-threatening, requires or prolongs hospitalization, is significantly or permanently disabling or incapacitating, constitutes a congenital anomaly or birth defect, is medically significant, or requires medical or surgical intervention to prevent one of these outcomes (please see section 8.2.4 for a detailed definition).

Any SAE occurring in a subject from consent until his/her last study visit/phone-visit (scheduled or unscheduled) must be reported.

The Investigator will ensure that the SAE reporting form is completed and emailed/faxed by the Investigator to the Pharmacovigilance department, Mylan, within 24 hours of learning of the occurrence of any SAE, even if the SAE does not appear to be drug-related. The original SAE reporting form, together with the email/fax confirmation sheet, must be kept with the case report forms at the study site. More details are provided in the protocol.

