#### ***7.4.7. Adverse Events and Serious Adverse Events***

Adverse events and SAEs will be recorded as specified in the [SCHEDULE OF ACTIVITIES](#) from the time of signing the informed consent form until the end of the follow-up visit. After the follow-up visit, any SAEs reported by the patients will be recorded if they are deemed related to trial drugs by the Investigator.

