#### **7.4.9.3. Sponsor's Responsibility**

- For SAEs, Mylan will independently evaluate whether the SAE was drug-related or related to an adverse device effect.
- In the event that the information available in the eCRF is inadequate for root cause analysis, Mylan will send a questionnaire to the Investigator, asking for more details.
- All SAEs related to the use of the needle, which is a legally marketed device, will be recorded and reported to Mylan for investigation and reporting to the needle manufacturer, if deemed necessary, based on the outcome of the investigation.
- Information regarding the circumstances, evaluation, investigation and analysis of all device deficiencies will be included in the clinical study report (CSR).

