## **8.2 Definitions**

### ***8.2.1. Adverse Events***

An AE is defined as any untoward medical occurrence in a patient or clinical investigation patient administered a pharmaceutical product that does not necessarily have a causal relationship with the product. An AE can therefore be any unfavorable and unintended sign (including a new, clinically important abnormal laboratory finding), symptom, or disease, temporally associated with drug administration, whether or not related to the product.

The above definition covers also cases of

- Exacerbation of pre-existing diseases or conditions.
  - Pre-existing diseases or conditions (reported at time of randomization in medical history) will not be considered AEs unless there is an increase in the frequency or severity, or a change in the quality of the disease or condition.

Events occurring in patients treated with the active comparator are also considered AEs. An AE will be defined as a treatment-emergent adverse event (TEAE) if the first onset (or worsening, in the case of pre-existing disease) is after the first administration of Mylan’s insulin glargine or Lantus® after randomization through follow-up visit or 28 days after last dose [for patients that do not have a follow-up visit].

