### **8.3 Management of Adverse Events**

AEs or SAEs will be collected from the time the patient signs the informed consent form until the end of the follow-up visit or phone-visit. Pre-existing diseases or conditions (reported at visit 1 in medical history) will not be considered AEs unless there is an increase in the frequency or severity, or a change in the quality of the disease or condition. An SAE deemed related to the trial drug by the Investigator in consultation with sponsor will be reported even after the follow-up visit if reported by patients. AEs and SAEs would also be recorded at phone calls. All SAEs should be immediately (within 24 hours) reported as per Section 8.3.2.8.

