### **8.3.2.8. Notification**

For SAEs, the active reporting period to Mylan, begins from the time that the patient provides informed consent, which is obtained prior to the patient's participation in the trial, i.e., prior to undergoing any trial-related procedure and/or receiving investigational product, through and including the follow up visit. Should an Investigator be made aware of any SAE occurring any time after the active reporting period, the SAE must be promptly reported to Mylan only in case of reasonable causality (i.e. suspected ADR).

The SAE reporting form (paper form only) is to be completed for all serious adverse events, signed by the Investigator, and emailed or faxed with supporting documentation (e.g., CRFs, hospital records, laboratory reports). Patient identity details (such as but not limited to name or clinic/hospital number) must not be visible on SAE forms or any supporting documentation provided by the Investigator. These should be "blacked out", and replaced with the site and patient's trial identification number on every page.

At that time of first notification, the Investigator/designee should provide the following information via the SAE report form:

- Protocol number
- Reporter (trial site and Investigator)
- Suspected trial treatment
- Patient's trial number
- SAE term
- The seriousness criteria that were met
- Investigator's opinion of the relationship to the trial treatments
- Severity

- Patient's age
- Date of first dose of trial treatment
- Date of last dose of trial treatment, if applicable
- Start and stop (if applicable) of the event (date and time)
- A brief description of the event, outcome to date, and any actions taken
- Concomitant medication at onset of the event
- Relevant past history information
- Relevant laboratory test findings

If the initial notification of an SAE is by telephone, within 24 hours of the initial telephone notification the Investigator must email the written SAE report form that describes the SAE to the Mylan Global Product Safety and Risk Management department.

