17.1. ADVERSE EVENTS

Adverse Events (AEs) will be coded using most updated MedDRA central coding dictionary, when it is available at time of analysis is conducted.

An AE is defined as any untoward medical occurrence in a patient or clinical investigation patient administered a pharmaceutical product that does not necessarily have a causal relationship with the product. An AE can therefore be any unfavorable and unintended sign (including a new, clinically important abnormal laboratory finding), symptom, or disease, temporally associated with drug administration, whether or not related to the product.

The above definition covers also cases of

- Exacerbation of pre-existing diseases or conditions.
 - Pre-existing diseases or conditions (reported at time of screening in medical history) will not be considered AEs unless there is an increase in the frequency or severity, or a change in the quality of the disease or condition.

An AE will be defined as treatment emergent (TEAE) if the first onset (or worsening in the case of pre-existing disease) is after the first administration of Mylan's insulin glargine sequence group or Lantus® sequence group (i.e. after the randomization) through 28 days after the last dose.

Document:	\\JEEDC-NAS01A\Biosdata\Mylan\INSULIN_GLARGINE\UXA25824\Biostatistics\Documentation\SAP		
Author:	[name] and [name]	Version Number:	Final V1.0
		Version Date:	[27JUL2016]

Template No: CS_TP_BS016 – Revision 3
Effective Date: 01May2012

Reference: CS_WI_BS005

See Appendix 1 for handling of partial dates for AEs. In the case where it is not possible to define an AE as treatment emergent or not, the AE will be classified by the worst case; i.e. treatment emergent.

An overall summary of number of patients for each treatment period within each of the categories described in the sub-section below, will be provided as specified in the templates.

Treatment sequence group comparison will be performed using Fisher's exact test for each treatment period. P-value for the corresponding two-sided test will be presented.

Listings will include TEAEs and Non-TEAEs.

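### For some early leavers with no follow-up visit, required AE and SAE collection can stop up to 28 days before the treatment-emergent window closes

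*Protocol*

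**What the plan says.** **When collection ends.** The Protocol gives more than one end point.

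- Contact Details for Reporting Serious Adverse Events: "Any SAE occurring in a subject from consent until his/her last study visit/phone-visit (scheduled or unscheduled) must be reported".
- Section 7.4.7: AEs and SAEs are recorded "from the time of signing the informed consent form until the end of the follow-up visit".
- Section 8.3: they are collected "until the end of the follow-up visit or phone-visit".
- Section 8.3.2.8: the active SAE reporting period runs "through and including the follow up visit". If the investigator learns of an SAE that occurs after this period, "the SAE must be promptly reported to Mylan only in case of reasonable causality".

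**What counts as treatment-emergent.** Protocol 8.2.1 counts events "through follow-up visit or 28 days after last dose [for patients that do not have a follow-up visit"; the 28-day limit is therefore only for patients without a follow-up visit. SAP 17.1 applies one limit to all patients: "i.e. after the randomization) through 28 days after the last dose". The algorithm in SAP Appendix 1 compares dates with the start of study medication only and sets no upper limit.

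**Who is followed after leaving early.** Protocol 6.2 makes follow-up of a patient who discontinues optional and subject to consent. Only withdrawal criteria 4 (safety issues) and 5 (illness, surgery or an SAE) add that the site should keep to the Schedule of Activities up to the week 40 call. If a patient also withdraws consent for disclosure of future information, nothing more may be collected.

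**The concern.** Section 8.2.1 expects that some patients will have no follow-up visit and gives them a 28-day treatment-emergent window. The sections on collection give no matching instruction: one ends reporting at whatever contact was last, and three end it at a visit these patients do not have. A patient who leaves at a clinic visit could pass most or all of the window with nobody required to ask about adverse events.

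This bears on the safety comparison. Adverse events are a secondary objective. SAP 17.1 compares the numbers of patients with TEAEs between sequence groups by Fisher's exact test, so an event that was never collected counts as no event. Treatment is open-label, and early leaving could differ between the groups.

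There is also a reporting consequence. Section 8.2.2 makes an event an adverse drug reaction if either the investigator or the sponsor judges it related, and 7.4.9.3, in the device section, says "For SAEs, Mylan will independently evaluate whether the SAE was drug-related or related to an adverse device effect". The sponsor cannot form its own view of an SAE that it was never sent. Severe hypoglycemia is one example, since 7.5.6.1 always classes it as serious.

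**Working it through.** **1. The plan's own figure.** The Schedule of Activities puts the end-of-treatment visit at day 252 ± 7 and the follow-up call at day 280 ± 7. The nominal interval is 280 − 252 = 28 days. This agrees with the 4-week follow-up period in 3.1 and the 28-day limit in 8.2.1 and SAP 17.1.

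**2. Early leaver with no follow-up visit.** Let g be the days from last dose to last contact. On the contact page's end point:

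uncovered days = max(0, 28 − g)

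| g (days) | Uncovered days |
|---|---|
| 0 | 28 |
| 7 | 21 |
| 14 | 14 |
| 21 | 7 |
| 28 or more | 0 |

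The maximum is 28, reached when the last contact falls on the day of the last dose.

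**3. Early leaver followed to the week 40 call (criteria 4 and 5).** The earliest call is day 280 − 7 = 273. A last dose on or before day 245 gives at least 273 − 245 = 28 days of follow-up, so nothing is uncovered.

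**4. Completers, assuming the last dose is on the end-of-treatment day.** The shortest interval to the call is (280 − 7) − (252 + 7) = 14 days. The longest is (280 + 7) − (252 − 7) = 42 days.

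- Under Protocol 8.2.1 the window ends at the follow-up visit, so there is no gap.
- Under SAP 17.1, up to 28 − 14 = 14 counted days can fall after the call, and up to 42 − 28 = 14 collected days can fall outside the window. This comes from the two documents' different treatment-emergent rules, not from the collection rule.

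**5. Which leavers fall in the gap.**

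- Criteria 4 and 5: followed to week 40, so normally not affected.
- Criterion 2 (pregnancy): separate follow-up to delivery or termination under 6.2 and 8.4.1, so less affected.
- Criterion 3 (repeated non-compliance): no follow-up instruction, so exposed.
- Criterion 1 (withdrawal of consent): exposed if the patient has not also withdrawn consent for future information. Otherwise collection is barred and no change of wording can help.

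**6. What goes uncollected.** Sections 7.4.7, 8.3 and 8.3.2.8 keep related SAEs reportable after the period ends. The gap therefore covers non-serious AEs and SAEs that the investigator does not consider related.

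**7. After the fix.** If the last required contact is at least 28 days after the last dose, the formula gives max(0, 28 − 28) = 0.

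**The case against.** The strongest reply is that the affected group is small and the reading narrow. Patients who leave for safety reasons, illness, surgery or an SAE are sent to the week 40 call. Section 6.2 allows any leaver to be followed with consent, and it obliges investigators to try to reach patients who miss visits. AEs and SAEs are also recorded at phone calls, and the contact page counts unscheduled calls, so any later contact moves the end date back. The contact page itself points to the protocol for detail, and the three numbered sections leave the end undefined for a patient without a follow-up visit; they do not place it at the last dose.

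Much of this stands. It makes 28 days a worst case and narrows the group. It does not close the gap. The contact attempt under 6.2 is meant to rule out an AE as the cause of withdrawal. It is not timed to 28 days after the last dose, and it does not reach a patient who leaves at an attended visit. An undefined end date also schedules no contact.

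Three stronger readings are tempting, and the documents do not support them.

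- **Post-treatment safety data are lost from the patients most likely to show a signal.** Criteria 4 and 5 cover those patients and direct follow-up to week 40.
- **The sponsor is excluded from causality after the last visit.** Section 8.3 has the investigator judge relatedness of later SAEs in consultation with the sponsor, and related ones are still reported. What the sponsor may not see is an SAE considered unrelated and therefore not sent.
- **A known amount of unobserved time enters the analysis as event-free.** One might take the 10% in 9.1 (0.10 × 138 = 13.8, about 14 patients) and multiply by 28 to get 392 patient-days. That 10% concerns missing baseline or last-period HbA1c, not early leaving. The TEAE analyses are patient incidences, and no planned analysis counts patient-days.

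The point rests on current text only; the superseded wording in the Document History is not evidence for it.

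**Conclusion.** The mismatch is real but narrow. It holds for patients who leave early, have no follow-up visit, fall outside criteria 4 and 5, and still permit future information to be collected. For each of them, between 0 and 28 treatment-emergent days can lack required collection, depending on when the last contact falls. Both the Protocol and the SAP count those days.

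The number of such patients cannot be derived from the documents and could be close to zero. The effect on the TEAE comparison therefore cannot be sized; its direction is that uncollected events lower the recorded incidence. The 28-day maximum assumes that the last contact is on the day of the last dose and that no later call takes place. This is a cheap improvement to the plan, not a flaw that threatens the primary result.

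**What to change.** In the contact page, 7.4.7, 8.3 and 8.3.2.8, state that for patients without a follow-up visit who have not withdrawn consent for future information, AE and SAE collection runs to 28 days after the last dose. Add one telephone call, in the existing Visit 14 format (AEs, SAEs and allergic reactions), at or after that day. All four places need the change; leaving one out would create a new contradiction.

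Keep the completers' end point at the follow-up visit. A general rule of 28 days for everyone would leave up to 14 required days with no planned contact when the visit windows bring the call forward.

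Align SAP 17.1 with Protocol 8.2.1, and add the same upper limit to the SAP Appendix 1 algorithm.

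The cost is a sentence in each of four places, a matching SAP edit, one call per affected patient, and a few extra unrelated SAE reports to process.

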## LIST OF ABBREVIATIONS

Abbreviation	Definition
ADA	American Diabetes Association
ADR	adverse drug reaction
AE(s)	adverse event(s)
ALT	alanine transaminase
ANCOVA	analysis of covariance
AST	aspartate transaminase
BMI	body mass index
CI	confidence interval
CMH	Cochran-Mantel-Haenszel
CRF	case report form
DCCT	Diabetes Control and Complications Trial
DNA	deoxyribonucleic acid
ECG	Electrocardiogram
eCRF	electronic case report form
EOT	end of treatment
FDA	Food and Drug Administration (United States)
FPG	fasting plasma glucose
GCP	Good Clinical Practice
HbA1c	glycosylated hemoglobin
HBsAg	hepatitis B surface antigen
HCP	host cell protein
HIPAA	Health Insurance Portability and Accountability Act
HIV	human immunodeficiency virus
IB	Investigator's brochure

Abbreviation	Definition
ICF	informed consent form
ICH	International Conference on Harmonisation
IEC	independent ethics committee
IRB	institutional review board
ITT	Intention to treat
IU	International Unit
IVRS	interactive voice response system
IWRS	interactive web response system
JNC	Joint National Committee
LDL	low density lipoprotein
LOCF	last observation carried forward
MDP	manic depressive psychosis
MedDRA	Medical Dictionary for Regulatory Activities
NAb	neutralizing antibody
NPH	neutral protamine Hagedorn
PD	pharmacodynamic(s)
PK	pharmacokinetic(s)
PP	Per protocol
SAE(s)	serious adverse event(s)
SD	standard deviation
SMBG	self-monitored blood glucose
T1DM	type 1 diabetes mellitus
T2DM	type 2 diabetes mellitus
WHO	World Health Organization

---

**PROTOCOL SYNOPSIS**

Title	An Open-label, Randomized, Multi-center, Parallel-Group Clinical Trial Comparing the Efficacy and Safety of Mylan’s Insulin Glargine with Lantus® in Type 1 Diabetes Mellitus Patients: An Extension Study
Objectives	
To compare the following variables when Mylan’s insulin glargine and Lantus® are interchanged:
 
Primary objective
 
 
• Demonstrate the equivalence of changes in HbA1C between two treatment sequence groups
 
 
Secondary objective
 
 
• Change in basal insulin dose per unit body weight (U/Kg/day)
 
• Immunogenicity: incidence and change from baseline in the relative levels of ADA, incidence and change from baseline in the relative levels of anti-HCP antibodies.
 
• Rate of hypoglycemic events per 30 days and occurrence of hypoglycemia
 
• Occurrence of local reactions, systemic reactions and other adverse events
 
• Change in fasting plasma glucose
 
• Change in 8-point SMBG profile
 
• Device-related safety assessments
 

Proposed Number of Sites	From approximately 70 selected sites, approximately 69 patients will be included in each arm, with a target of approximately 138 randomized patients in both arms together.
Study Population	Patients with an established diagnosis of T1DM per ADA 2014 criteria who were randomized to the Lantus® treatment arm of the MYL-GAI-3001 study, and who have completed the 52-week treatment period on Lantus® will be eligible to be screened for the MYL-1501D-3003 study.
Duration of Patient Participation	
The maximum possible duration of patient participation in the extension study is approximately 40 weeks, which includes:
 
 
1. Randomized comparative treatment period 1: 12 weeks.
 
2. Randomized comparative treatment period 2: 12 weeks.
 
3. Randomized comparative treatment period 3: 12 weeks.
 
4. Follow-up period: 4 weeks.
 

Study Design	
This multi-center, open-label, randomized clinical extension study in patients with T1DM will assess interchangeability of Mylan’s insulin glargine and Lantus® with respect to safety and efficacy.
 
Patients with an established diagnosis of T1DM per ADA 2014 criteria who were randomized to the Lantus® treatment arm of the MYL-GAI-3001 study, and who have completed the 52-week treatment period on Lantus® will be eligible to be screened for the MYL-1501D-3003 study.
 
There will be 2 treatment arms (with 3 sequences) in the extension study.
 
Patients randomized to Lantus® during MYL-GAI-3001 will be randomized to either Lantus® or Mylan’s insulin glargine for 12 weeks. After this first 12 weeks of treatment, those on Mylan’s insulin glargine will be switched to Lantus® while those on Lantus® will continue on Lantus® for another 12 weeks to complete the second treatment period. After 24 weeks of treatment, those patients who were randomized to Mylan’s insulin glargine and had a switch to Lantus® will undergo an additional switch to Mylan’s insulin glargine for an additional 12 weeks to complete the third treatment period. Those patients who are on Lantus® since the start of the study and did not have any switch, will continue on Lantus® for another 12 weeks to complete the third

	
treatment period.
 
After 36 weeks of treatment, patients will go back to the approved medications (as prescribed) and will be followed up for safety for another 4 weeks (Mylan will not provide any medications from 36 weeks of treatment onwards). The 36 to 40 week safety data will also be captured.
 
During the 36-weeks treatment period, the titration (if needed) of both Mylan's insulin glargine and Lantus® should be kept to a minimum, unless there are safety concerns.
 
The week 52 visit for MYL-GAI-3001 will also serve as the week 0 visit for the extension study.

Number of Patients	From approximately 70 selected sites, approximately 69 patients will be included in each arm, with a target of approximately 138 randomized patients in both arms together.
Inclusion Criteria	
Patients must meet all of the following inclusion criteria to be eligible for enrollment into the extension study:
 
 
1. Patients who have completed the 52-week treatment period (irrespective of their age at the completion of MYL-GAI-3001) of MYL-GAI-300 and were assigned to Lantus® in MYL-GAI-3001.
 
2. Patients or their legal representatives must give written and signed informed consent before starting any protocol-specific procedures.
 
3. The patient is able and willing to comply with the requirements of the extension study protocol including the 8-point SMBG, completion of the patient diary records as per the instructions and following a recommended diet and exercise plan for the entire duration of the extension study.
 
4. Female patients complying with the following: 
 
o Female patients of childbearing potential must be using oral contraception or two other acceptable methods of contraception (e.g., intra-uterine device plus condom, spermicidal gel plus condom, diaphragm plus condom, etc.) from the time of randomization throughout the entire study.
 
o Periodic abstinence (e.g., calendar, ovulation, symptothermal, post-ovulation methods) and withdrawal are not acceptable methods of contraception.
 
o Postmenopausal females must have had no menstrual bleeding for at least 1 year prior to inclusion to MYL-1501D-3003.
 
o Female patients who report surgical sterilization must have had the procedure at least 6 months prior to inclusion to MYL-1501D-3003.
 
o All female patients of childbearing potential, must have negative pregnancy test results at baseline (week 0) and at each clinic visit as per the SCHEDULE OF ACTIVITIES.
 
o If female patients have male partners who have undergone vasectomy, the vasectomy must have occurred more than 6 months prior to inclusion in MYL-1501D-3003.
 
 
 

Exclusion Criteria	
Patients meeting any of the following criteria will not be included in the extension study:
 
 
1) History or presence of a medical condition or disease that in the Investigator's opinion would place the patient at an unacceptable risk from trial participation.
 
2) History of clinically significant (i.e., significant enough to alter the insulin dose requirement, as per the Investigator) acute bacterial, viral or fungal systemic infections in the 4 weeks prior to inclusion / randomization (recorded while collecting patient history) in the MYL-1501D-3003 extension study.
 
3) Patients scheduled to receive another investigational drug during the extension study period.
 
4) Any major elective surgery requiring hospitalization planned during the extension study period.
 
5) Moderate insulin resistance, defined as requiring insulin (Basal + Prandial) of <math>\geq 1.5</math> U/kg/day (Lantus® in U/kg/day or Mylan's insulin glargine in IU/kg/day).
 

Withdrawal Criteria	If, for any reason, a patient discontinues the trial prematurely, the patient may be followed up

	
upon consent and as described in the following withdrawal criteria: Following are the withdrawal criteria:
 
 
1. Withdrawal of consent.
 
2. For female patients, diagnosis of pregnancy or stated intention to become pregnant. Effort should be made so that the pregnant women still report to the site and are followed until delivery or termination.
 
3. Repeated protocol non-compliance.
 
4. At the investigator's discretion, (following discussion with the sponsor medical monitor), for safety issues such as severe hypoglycemia or hypoglycemic unawareness. The site should follow-up these patients as per the SCHEDULE OF ACTIVITIES until the 40 week follow-up call.
 
5. At the investigator's discretion, (following discussion with the sponsor medical monitor), in certain situations such as significant intercurrent illness, hospitalization for surgery, or an SAE. The site should follow-up these patients as per the SCHEDULE OF ACTIVITIES until the 40 week follow-up call.
 
				

Study Treatments
	
Investigational Products
 
 
• Mylan's insulin glargine (test product) 100 IU/mL
 
• Lantus® from Sanofi-Aventis sourced from the US (US listed drug) 100 U/mL
 
 
Both investigational products will be provided in a pre-filled disposable pen with a 3 mL cartridge.
 
Mealtime insulin
 
 
• Humalog® (insulin lispro injection, 100 U/mL), manufactured by Eli Lilly (administered in Humalog Kwikpen® disposable pens).
 
 
All patients will continue on insulin lispro for the complete trial. The Investigator will inform the patients of the doses to be used and the titration scheme to be followed (if needed during the study). During the trial period dose titration (if needed) will be kept to a minimum.
				

Concomitant Medications and Therapy
	
Other than study drugs, insulin, insulin analogs and other anti-diabetes medications as well as glucocorticoid therapy (oral, intravenous, inhaled or other routes that produce systemic effects) should not be taken during the study (prohibited medications).
 
A list of restricted medications that may interfere with the effect of insulin is given in the below table. No drugs listed in this table should be started during the treatment period.
 
All treatments being taken by the patients following signing the ICF in addition to the trial treatment (investigational products and mealtime insulin) during the trial are regarded as concomitant medications and must be documented in the CRF. Mylan's insulin glargine, Lantus® and insulin lispro will not be considered as concomitant medications.
 
  
 Drug classes that are known to augment the blood glucose lowering effect of insulin such as:	Drugs and drug classes that are known to decrease the blood glucose lowering effect of insulin such as:	
   
  
 
1. salicylates at doses more than >2 g/day
 
2. sulfa antibiotics
 
3. angiotensin converting enzyme inhibitors
 
4. disopyramide
 
5. fibrates
 
6. fluoxetine
 
7. monoamine oxidase inhibitors
 
 	 
 
1. danazol
 
2. niacin
 
3. diuretics
 
4. sympathomimetic agents
 
5. glucagon
 
6. isoniazid
 
7. somatropin
 
8. thyroid hormones
 
9. oral contraceptives
 
 	
  
	Drug classes that are known to augment the blood glucose lowering effect of insulin such as:	Drugs and drug classes that are known to decrease the blood glucose lowering effect of insulin such as:	
 
1. salicylates at doses more than >2 g/day
 
2. sulfa antibiotics
 
3. angiotensin converting enzyme inhibitors
 
4. disopyramide
 
5. fibrates
 
6. fluoxetine
 
7. monoamine oxidase inhibitors
 
	
 
1. danazol
 
2. niacin
 
3. diuretics
 
4. sympathomimetic agents
 
5. glucagon
 
6. isoniazid
 
7. somatropin
 
8. thyroid hormones
 
9. oral contraceptives
 

Drug classes that are known to augment the blood glucose lowering effect of insulin such as:	Drugs and drug classes that are known to decrease the blood glucose lowering effect of insulin such as:				

 
1. salicylates at doses more than >2 g/day
 
2. sulfa antibiotics
 
3. angiotensin converting enzyme inhibitors
 
4. disopyramide
 
5. fibrates
 
6. fluoxetine
 
7. monoamine oxidase inhibitors
 
	
 
1. danazol
 
2. niacin
 
3. diuretics
 
4. sympathomimetic agents
 
5. glucagon
 
6. isoniazid
 
7. somatropin
 
8. thyroid hormones
 
9. oral contraceptives
 
				

	

8. propoxyphene

9. pentoxifylline

10. somatostatin analogs

11. bromergocryptine (bromocryptine)

12. anabolic steroids.

	

10. estrogens

11. progestogens

12. protease inhibitors

13. phenothiazine derivatives

14. atypical antipsychotic medications (e.g. olanzapine and clozapine).

--	--	--

